6.9.1. Adverse Events

[figure not shown]
The safety data will be summarized in accordance with CaPS. All safety data will be summarized descriptively through appropriate data tabulations, descriptive statistics, categorical summaries, and graphical presentations. Safety endpoints for the study include:

- Treatment-emergent AEs and SAEs;
- Withdrawals from active treatment due to AEs;
- Serious infections, defined as any infection (viral, bacterial, and fungal) requiring hospitalization or parenteral antimicrobials.

Treatment-emergent AEs will also be analyzed using a 3-tier approach. Risk differences between the active treatments and placebo will be used to summarize the results.

For Tier-1 events, point estimates, 95% confidence intervals and p-values will be presented graphically comparing each active dose group with placebo. No multiplicity adjustments will be made. For Tier-2 events, only point estimates and 95% confidence intervals will be presented graphically (see [Section 5.2.6](#)). Tier-3 events will be summarized as part of the overall AE summaries, AEs will be displayed by MedDRA system organ class (SOC).

It should be recognized that most studies are not designed to reliably demonstrate a causal relationship between the use of a pharmaceutical product and an adverse event or a group of adverse events. Except for select events in unique situations, studies do not employ formal adjudication procedures for the purpose of event classification. CCI

6.9.2. Laboratory Data

Laboratory data will be listed and summarized in accordance with the CaPS reporting standards. Summaries of subjects meeting pre-specified monitoring and discontinuation criteria will be created using methods for categorical data (see [Section 5.2.4](#)).

6.9.3. Vital Signs, including Height and Weight

Vital signs will be summarized at baseline, Weeks 2, 4, 8, and 12/End of Treatment visits. Height and weight will be summarized at baseline and End of Treatment visits.

6.9.4. Electrocardiogram

ECG parameters, if applicable, will be summarized at baseline and End of Treatment visits.

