- x. A single 12-lead ECG will be performed at screening and all other on-site visits and interpreted by a central reader. Clinically significant or exclusionary ECG findings at the screening or baseline visits will require screen failure.
- y. DLQI will be completed by adult subjects only. Adolescents 12-17 years of age will complete the CDLQI instead.

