7.2.5. Electrocardiogram

A single 12-lead ECG will be collected at screening and all other on-site visits as specified in the [Schedule of Activities](#). ECGs reading will be performed by a central reader.

All scheduled ECGs should be performed after the subject has rested quietly for at least 10 minutes in a supine position.

A subject's screening ECG must be within normal limits prior to randomization.

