3.5.3. Vital Signs, including Height and Weight

Vital sign measurements are oral or tympanic temperature, respiratory rate, pulse rate and blood pressures.

Height and weight are collected at pre- and post-treatment.

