6.9. Safety Summaries and Analyses

Safety analyses will be based on the SAF analysis set.

All clinical AEs, SAEs, TEAEs, withdrawal due to AEs, ECGs, vital signs and safety laboratory data will be reviewed and summarized on an ongoing basis during the study to evaluate the safety of subjects.

Safety data will be presented in tabular and/or graphical format and summarized descriptively, where appropriate. All safety endpoints will be listed and summarized in accordance with CaPS. Categorical outcomes (e.g., AEs) will be summarized by subject counts and percentage. Continuous outcome (e.g., blood pressure, pulse rate, etc.) will be summarized using N, mean, median, standard deviation, etc. Change from baseline in laboratory data, ECGs and vital signs will also be summarized. Subject listings will be produced for these safety endpoints accordingly.

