6.9.5. Physical Examination

Physical examinations will be summarized at baseline and all-available post-baseline visits.

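### SAP 6.9.4 names only baseline and End of Treatment for ECG summaries, so three of the four scheduled on-treatment ECG visits (Weeks 2, 4 and 8) have no committed by-visit summary

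*SAP*

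**What the plan says.** **Collection.** Footnote x of the protocol's Schedule of Activities states: "A single 12-lead ECG will be performed at screening and all other on-site visits and interpreted by a central reader". Protocol 7.2.5 agrees: "A single 12-lead ECG will be collected at screening and all other on-site visits". The schedule marks an ECG at screening, Day 1, Weeks 2, 4, 8 and 12 (or early termination) and the Week 16 follow-up. Weeks 1 and 6 are telephone calls.

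**Specific summary rule.** SAP 6.9.4: "ECG parameters, if applicable, will be summarized at baseline and End of Treatment visits".

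**Neighbouring rules.** SAP 6.9.3: "Vital signs will be summarized at baseline, Weeks 2, 4, 8, and 12/End of Treatment visits". SAP 6.9.5: "Physical examinations will be summarized at baseline and all-available post-baseline visits".

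**General text.** SAP 3.5 lists ECG abnormality incidence and ECG change from baseline among the safety endpoints. SAP 6.9 commits to ongoing review ("ECGs, vital signs and safety laboratory data will be reviewed and summarized on an ongoing basis during the study") and adds: "Change from baseline in laboratory data, ECGs and vital signs will also be summarized". It refers the presentation of all safety endpoints to CaPS, which is not reproduced in these documents. SAP Appendix 2 applies visit windows to ECG data if by-visit statistics are needed.

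**The concern.** ECG is a listed safety endpoint. Protocol Appendix 4 also contains a QTcF discontinuation criterion that applies throughout the study. Protocol 1.4 mentions six Phase 1 subjects, five on active drug and one on placebo, whose QTcF met a threshold for absolute value or change. It gives no denominators, so this shows why QTcF deserves attention but is not evidence of an effect.

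Against that background, a visit rule naming one on-treatment time point gives a thin description of the ECG data. A mean QTcF shift at Week 2 or 4 that faded by Week 12, or individual changes that stayed below the discontinuation criterion and were gone by End of Treatment, would not show in the two-visit summary. At stake is how completely the arms are described on a safety endpoint.

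**Working it through.** There is no figure in the plan to reproduce. The check is a count, followed by a comparison of sections.

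**Step 1. Count the visits.** Scheduled on-treatment ECG visits (Schedule of Activities; Protocol 6.2.3, 6.2.4, 6.2.6 and 6.2.7) are Weeks 2, 4, 8 and 12, so 4. Named in SAP 6.9.4: End of Treatment (Week 12 or early termination), so 1. Not named: 4 − 1 = 3, and 3/4 = 75%. Week 16 is off treatment and is left out.

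**Step 2. Compare with the neighbouring sections.**

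| Measure | Collected after baseline, on treatment | Summary visits named in the SAP |
|---|---|---|
| Vital signs (6.9.3) | Weeks 2, 4, 8, 12 | Weeks 2, 4, 8, 12/End of Treatment |
| Height and weight (6.9.3) | Week 12 | End of Treatment |
| ECG (6.9.4) | Weeks 2, 4, 8, 12 | End of Treatment |
| Physical examination (6.9.5) | Weeks 2, 4, 8, 12 | All available post-baseline visits |

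Height and weight have the same two-point rule as the ECG, but there it fits the data: SAP 3.5.3 notes "Height and weight are collected at pre- and post-treatment". Of the measures in 6.9.3 to 6.9.5, only the ECG has intermediate readings that its stated rule does not mention.

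**Step 3. Look for other text that commits to Weeks 2, 4 and 8.**
- SAP 3.5 and 6.9 require ECG abnormality incidence and change from baseline. Neither names or restricts visits.
- SAP Appendix 2 makes by-visit ECG statistics conditional.
- SAP 6.9.2 summarises subjects who meet monitoring and discontinuation criteria, but it sits under Laboratory Data. It does not say whether the QTcF criterion is included.

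None of these commits the sponsor to an ECG summary at Weeks 2, 4 or 8, and none prevents one.

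**Step 4. Repeat the count after the repair.** If 6.9.4 named the visits in 6.9.3, 4 of 4 on-treatment ECG visits would have a committed summary, against 1 of 4 now.

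**The case against.** The strongest reply is that 6.9.4 sets a minimum. It contains no word of exclusion, and Appendix 2 would have no reason to provide ECG visit windows if by-visit ECG output were ruled out. This stands: a reader might infer that the SAP forbids ECG summaries at Weeks 2, 4 and 8, and the text does not support that.

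A second reply is that an abnormality seen only at Week 4 can still be counted. SAP 3.5 makes abnormality incidence an endpoint without a visit limit, and 6.9 says safety endpoints are summarised, with categorical outcomes as counts and percentages. This also stands. It would be wrong to conclude that such an event escapes every planned summary. It may also enter the adverse event tables under Protocol 8.2.2, and a subject who discontinues still has an end-of-treatment visit with an ECG (Protocol 6.2.7 and 6.4).

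Third, an unnamed visit in this SAP does not prove an unsummarised one: 6.9.2 names no visits for laboratory data and relies on CaPS. That is fair, but the cases differ. Section 6.9.2 leaves the visits to the standard, whereas 6.9.4 states a visit rule of its own and leaves three visits out of it.

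Fourth, there is no conflict with the protocol. Protocol 9.3 lists ECG parameters with the same conditional wording and promises extra change-from-baseline summaries only for laboratory data and vital signs. The SAP goes further by adding ECG change from baseline. This stands, so the point is an improvement to the plan and not a departure from the protocol.

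**Conclusion.** The point holds in a limited form. Three of four scheduled on-treatment ECG visits (75%) have no committed by-visit summary, although the data are collected and centrally read and the adjacent sections cover the same visits for other measures. What is left unsecured is the by-arm time course and any QTcF change that is transient or below the criterion.

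The 75% counts visits. It does not measure missed signals, and the documents give no basis for estimating any effect on the safety conclusions. A reader might infer that a QTcF signal would be missed or that subjects are less well protected. The documents support neither: abnormality counts, listings, individual monitoring, central reading, ongoing review and the external data monitoring committee are untouched. So are efficacy, alpha and power.

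The conclusion assumes that a section-specific visit rule is what the programmers will follow. CaPS may already supply by-visit or maximum-QTcF tables. These documents do not show it, and nothing here claims that such tables are absent.

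**What to change.** Amend SAP 6.9.4 to summarise ECG parameters and QTcF change from baseline by treatment group at baseline and Weeks 2, 4, 8 and 12/End of Treatment, matching 6.9.3. Add a by-arm categorical summary of each subject's maximum post-baseline on-treatment QTcF and maximum change, using the sponsor's standard categories. If CaPS already provides these tables, a cross-reference in 6.9.4 is enough.

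As a clarification only, 6.9.2 could say whether its summary of discontinuation criteria includes the QTcF criterion. If it does, it should note that the criterion measures change from the screening ECG, whereas the general baseline in SAP 3.4 is Day 1.

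Cost: SAP wording and a few descriptive tables from data already collected. No new visits, procedures or hypothesis tests are needed.

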6.9.5. Physical Examination

Physical examinations will be summarized at baseline and all-available post-baseline visits.

7. INTERIM ANALYSES

There will be no interim analyses for this study.

This study uses an External Data Monitoring Committee (E-DMC). The E-DMC will be responsible for ongoing monitoring of the efficacy, safety and PKs of subjects in the study according to the charter. Pharmacokinetic data from the first 20 adolescent subjects will be analyzed and reviewed by the E-DMC. The recommendations made by the E-DMC to alter the conduct of the study will be forwarded to Pfizer for final decision. Pfizer will forward such decisions, which may include summaries of aggregate analyses of endpoint events and of safety data that are not endpoints, to regulatory authorities, as appropriate. Composition of the E-DMC and processes under which the E-DMC operates will be documented in the E-DMC charter.

9. APPENDICES

Appendix 1. Summary of Clinical Efficacy Analyses

Efficacy Endpoints	Population	Analysis Method	Missing Data Imputation	Primary Analysis for Co-primary Endpoints
Week 12 IGA Response	FAS	CMH	NR	Yes
	PPAS	CMH	NR	No
	FAS	CMH	TP (MAR)	No
	FAS	CMH	TP (MNAR)	No
Week 12 EASI-75 Response	FAS	CMH	NR	Yes
	PPAS	CMH	NR	No
	FAS	CMH	TP (MAR)	No
	FAS	CMH	TP (MNAR)	No
Weeks 2, 4, 8 and 12 NRS4 for severity Response	FAS	CMH	NR+MI	
	PPAS	CMH	NR+MI	
	FAS	CMH	NR	
Week 12 CFBL in PSAAD	FAS	MMRM	OD	
	PPAS	MMRM	OD	
Time to NRS4 for severity	FAS	Kaplan-Meier	OD	
Weeks 2, 4 and 8 IGA Response	FAS	CMH	NR	
Weeks 2, 4, 8 and 12 EASI-50 / EASI-90 / EASI-100 Response	FAS	CMH	NR	
Weeks 2, 4 and 8 EASI-75 Response	FAS	CMH	NR	
Weeks 2, 4, 8 and 12 CFBL in Total EASI Score	FAS	MMRM	OD	
Weeks 2, 4, 8 and 12 CFBL in NRS for severity	FAS	MMRM	OD	
Weeks 2, 4, 8 and 12 CFBL in %BSA	FAS	MMRM	OD	
Weeks 2, 4, 8 and 12 CFBL in SCORAD Total Score	FAS	MMRM	OD	
Weeks 2, 4, 8 and 12 SCORAD50 / SCORAD75 Response	FAS	CMH	NR	
Weeks 2, 4, 8 and 12 CFBL in SCORAD subjective VAS assessments of sleep loss	FAS	MMRM	OD	

CFBL=Change from baseline; CMH=Cochran-Mantel-Haenszel; ANCOVA=Analysis of Covariance; MMRM=Mixed-effect Model Repeated Measures; NR=Non-Responder; TP=Tipping Point; OD=Observed Data; MI=Multiple Imputation; MAR=Missing At Random; MNAR=Missing Not At Random

090177e1912f28b6\Approved\Approved On: 26-Jun-2019 09:22 (GMT)

Appendix 2. Definition and Use of Visit Windows in Reporting

Visit windows will be used for efficacy variables, and for any safety data that display or summarize by study visit. For other endpoints (e.g., ECG, vital signs), visit windows will be applied for summary statistics by study visits if required.

Visit Label	Target Day	Definition [Day window]
Screening		Days -28 to Day -1
Baseline	Day 1 (Day of first dose)	Last observation prior to and including day of first dose
Week 2	15	Days 2 to 22
Week 4	29	Days 23 to 43
Week 8	57	Days 44 to 71
Week 12	85	Days 72 to 99
Follow Up/End of Study		
Week 16	-	Days 100 to -

For the lab values, if the calculated study day for the labelled baseline visit is not study Day 1, but falls within 28 days before the start of the study dosing, then that data should be used for the baseline instead of leaving baseline missing.

For the other values, if the calculated study day for the labelled baseline visit is not study Day 1, but falls before the start of the study dosing, then that data should be used for the baseline instead of leaving baseline missing.

If two or more visits fall into the same window, keep the one closest to the Target Day. If two visits are equaled distant from the Target Day in absolute value, the later visit should be used.

Safety analysis may follow CaPS standards.

090177e1912f28b6\Approved\Approved On: 26-Jun-2019 09:22 (GMT)

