1.2.4. Phase 2b in AD (B7451006)

B7451006 was a Phase 2b proof-of-concept trial in adults (ages 18-75) with AD investigating doses of 10, 30, 100, and 200 mg PF-04965842 or placebo taken once daily (QD) for up to 12 weeks. The primary endpoint in this study was the proportion of subjects achieving an IGA score of clear (0), or almost clear (1), and a ≥ 2 -point improvement from baseline at Week 12. The baseline was defined as the IGA score on Day 1 pre-dose.

At Week 12, IGA response rates of PF-04965842 100 mg and 200 mg dose groups were significantly greater than placebo in patients with moderate to severe AD. The IGA response rates of the 200 mg and 100 mg groups were 44.5% and 27.8%, compared to 6.3% in the placebo group, ($P= 0.0032$ and 0.0184 , respectively). The percent change from baseline (% CFB) in EASI scores at Week 12 were significantly higher for both the 200 mg and 100 mg groups compared to placebo ($P<0.0001$ and $P=0.0091$, respectively). PF-04965842 demonstrated a rapid onset of action. In the 200 mg group, IGA and EASI scores improved until week 4 and week 6, respectively, and maintained their effect through 12 weeks of treatment. Response rates at Week 12 for the 10 mg and 30 mg groups were not significantly different from placebo. A key differentiating feature for the JAK1 inhibitor is rapid resolution of itch associated with AD. Significant separation from placebo was achieved for the pruritus NRS score as early as 2 days after initiation of treatment for the 200 mg dose group.

Overall, the results demonstrated dose-dependent increases in responses at Week 12 for key efficacy endpoints (IGA, EASI and pruritus NRS score).

PF-04965842 appeared generally safe and well tolerated in this study. AEs and SAEs were numerically higher in subjects receiving PF-04965842 compared to placebo, but did not appear to increase with dose. The most common AEs were in the infections and infestations, skin and subcutaneous tissue disorders and gastrointestinal disorders system organ class (SOC), and the majority of the AEs were mild. There were 2 cases of herpes zoster, one in the 10 mg group (not treatment related), and one in the 30 mg group (treatment related). There were dose-dependent decreases in platelet counts observed in the study, which plateaued at Week 4, and were not generally clinically relevant. Further details of the clinical Phase 2 development program can be found in the Investigator's Brochure (IB).

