5.3.1. Binary Endpoints

For binary endpoints analyzed at each scheduled visit separately, visit windows (see [Appendix 2](#)) will be used to map all observed data into nominal visits. After mapping, for subjects who drop out for any reason or require a rescue medication, any missing data will be defined as “non-responsive” from that point on at all subsequent visits; for other subjects, any observations missing intermittently (including baseline values) will be considered missing completely at random (MCAR) and will remain missing in the analysis.

Additional analyses that are based on statistical considerations will utilize the longitudinal nature of the binary endpoint. A Generalized Linear Mixed Model (GLMM) will be fit to the observed data (i.e., without defining missing data due to dropout as “non-response”). The binary outcome will be modeled using a logistic-normal distribution. Fixed factors will include treatment (PF-04965842 200 mg QD and 100 mg QD and the placebo group), visit (Weeks 2, 4, 8 and 12) and treatment-by-visit interaction. Visit will be modeled as a categorical covariate. A subject-specific random intercept will be used to model the correlation within a subject over time (see [Appendix 3](#)). Missing observations for the active groups will be imputed multiply using a tipping point analysis to estimate the treatment effect under the assumption that the missing data mechanism is missing at random (MAR) or more generally, is missing not at random (MNAR). Using the estimated posterior predictive distribution of the GLMM model parameters obtained using Markov Chain Monte Carlo (MCMC) methods, estimates of the posterior predictive probability of response will be calculated for each treatment group. For subjects with missing data at a visit, the posterior predictive response probability in each PF-04965842 dose group will be re-defined as a weighted linear combination of the posterior predictive response probability from this group and the posterior predictive response probability from the placebo group, where the missing observations in placebo group are assumed to be missing at random (MAR) (see [Appendix 3](#)). These weights are fixed MNAR quantities for the active groups. A single imputation of the missing value will be sampled from a Bernoulli distribution with this corresponding shifted / re-defined probability of response for the PF-04965842 dose groups.

090177e1912f28b6\Approved\Approved On: 26-Jun-2019 09:22 (GMT)

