6.3. Key Secondary Endpoints

6.3.1. Weeks 2, 4 and 12 NRS4 for severity Response

- Summary: Proportion of subjects with NRS4 for severity response at Weeks 2, 4 and 12;
- Population: Subjects from the (FAS, PPAS) with a baseline NRS score for severity ≥ 4 ;
- Statistical Method: CMH and normal approximation in [Section 5.2.1](#). Visit windows will be used as described in [Appendix 2](#);
- Missing Data: Two analyses will be performed:
 - Primary Analysis: Missing data arising due to subject dropout are considered “non-response”. For any other missing observations, a multiple imputation

approach based on a GLMM will be used. (see the last two paragraphs within [Section 5.3.1](#)). This analysis will be based on both the FAS and the PPAS.

- Sensitivity Analysis: All missing data will be considered as “non-response”. This analysis will be based on the FAS only.

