Appendix 8. Pruritus and Symptoms Assessment for Atopic Dermatitis (PSAAD) (e-Diary)

The PSAAD is a daily patient-reported symptom diary. The preliminary version is a 15-item questionnaire that includes 11 items developed to measure symptoms of atopic dermatitis, capturing those identified by patients to be most important, based on a 24-hour recall.

Analysis of the PSAAD will be based solely on these 11 items. CCI

The PSAAD total score will be calculated as the simple arithmetic mean of items 1-11 as listed below. Items 12, 13, 14, and 15 will be only used to further validate PSAAD and they are not the part of the PSAAD scale itself.

For analyses included in this SAP, weekly averages of the PSAAD score will be used. For example, the baseline value is defined as a simple average of all observed values from Day -6 until Day 1, the Week 1 value is defined as a simple average of all observed values from Day 2 until Day 8, the Week 2 value is defined as a simple average of all observed values from Day 9 until Day 15, and so on and so forth up to Week 12.

Pruritus and Symptoms Assessment for Atopic Dermatitis (PSAAD)

Please answer each question by thinking about your skin condition (most often called atopic eczema or atopic dermatitis) over the past 24 hours. This includes today and last night.

For each question, think about all the areas of your body affected by your skin condition and choose the number that best describes your experience.

1) How itchy was your skin over the past 24 hours?

0	1	2	3	4	5	6	7	8	9	10
Not itchy										Extremely itchy

2) How painful was your skin over the past 24 hours?

0	1	2	3	4	5	6	7	8	9	10
Not painful										Extremely painful

3) How dry was your skin over the past 24 hours?

0	1	2	3	4	5	6	7	8	9	10
---	---	---	---	---	---	---	---	---	---	----

Not dry **Extremely dry**

4) How flaky was your skin over the past 24 hours?

0	1	2	3	4	5	6	7	8	9	10
Not flaky										Extremely flaky

5) How cracked was your skin over the past 24 hours?

0	1	2	3	4	5	6	7	8	9	10
Not cracked										Extremely cracked

6) How bumpy was your skin over the past 24 hours?

0	1	2	3	4	5	6	7	8	9	10
Not bumpy										Extremely bumpy

7) How red was your skin over the past 24 hours?

0	1	2	3	4	5	6	7	8	9	10
Not red										Extremely red

8) How discolored (darker or lighter) was your skin over the past 24 hours?

0	1	2	3	4	5	6	7	8	9	10
Not discolored										Extremely discolored

090177e1912f28b6\Approved\Approved On: 26-Jun-2019 09:22 (GMT)

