- l. A documented TB test performed within 12 weeks prior to Day 1 is acceptable. Subjects with a history of tuberculosis may not require TB testing as per the protocol exclusion criteria in Section 4.2. Perform TB test procedure using the QuantiFERON[®]-TB Gold In Tube Test (or Purified Protein Derivative). A negative PPD test can be substituted for the QuantiFERON[®]-TB Gold In-Tube test only if the central laboratory is unable to perform the QuantiFERON[®]-TB Gold In-Tube test or cannot determine the results to be positive or negative and the Pfizer Medical Monitor approves it on a case-by-case basis. In addition to protocol required TB testing, sites should follow their local standards for TB status determination, which may include chest X-ray. See Section 7.2.3.
- m. A pharmacokinetic (PK) blood sample will be collected prior to dosing at the study site on Week 4.
- n. PK blood samples will be collected at 0.5 hours (± 15 min) postdose at the Week 4 visit and at 0.5 hours (± 15 min) and 4.0 hours (± 30 min) postdose at the Week 12 visit (EOT/ET). For ET visits, if the subject discontinues before Week 4 do not collect PK samples. If the ET visit occurs after Week 4, collect PK samples only if the subject takes the investigational product at the site visit.
- o. Subjects should take the medication from study Days 1 to 85. Subjects will be encouraged to take the medication in the morning whenever possible; however, at study visit days, subjects are to be instructed to refrain from dosing at home, and are to take the dose in the clinic.
- p. Site staff is to administer the C-SSRS, SBQ-R and PHQ-8 to all subjects at screening and score immediately. Subjects who have recent or active suicidal ideation or behavior or clinically significant depression will be excluded from the study or discontinued from the study per Section 4.2, Section 7.4.1, Section 7.4.2 and Section 7.4.3.
- q. Pruritus Numerical Rating Scale (NRS) will be assessed using an eDiary, daily during the screening period and from Day 1 to 15. After Day 15, the pruritus NRS will be completed only on study visit days in the eDiary. At the Screening visit, site staff will dispense the ePRO device and review instructions for completion of the subject eDiary for the NRS. At every visit, the study coordinator will review the eDiary for completeness and counsel the subject on how to complete the items in the daily eDiary, if needed.

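### Read as written, the Days 2 to 22 window lets an early daily-diary itch score stand as the alpha-controlled Week 2 NRS4 result for subjects who drop out or stop the diary early

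*SAP*

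**What the plan says.** - **Endpoint and alpha.** Week 2 NRS4 for 200 mg against placebo is tested at 2.5% once the 200 mg co-primaries succeed. Its result decides whether Sequence A is tested at 5% or 2.5% (SAP 5.1).
- **Collection.** SAP Appendix 9, in the schedule note on this scale: "Pruritus Numerical Rating Scale (NRS) will be assessed using an eDiary, daily during the screening period and from Day 1 to 15". Later scores are taken on study visit days only.
- **Window.** SAP 6.3.1 says of NRS4: "Visit windows will be used as described in" Appendix 2. There, Week 2 has target Day 15 and runs from Day 2 to Day 22. The selection rule is "If two or more visits fall into the same window, keep the one closest to the Target Day", and the later record wins a tie.
- **Order of operations.** SAP 5.3.1 says the windows "will be used to map all observed data into nominal visits". It continues: "After mapping, for subjects who drop out for any reason or require a rescue medication, any missing data will be defined as" non-response from then on. For NRS4, multiple imputation covers only what is still missing for other reasons.
- **Protocol.** Section 9.2.3 treats a subject who has withdrawn as a non-responder at later assessments, and 9.2.4 carries that method over to NRS4. The protocol's own Week 2 visit is Day 15 ±1.
- **The other daily diary.** For PSAAD, SAP Appendix 8 has a bin suited to daily data: "the Week 2 value is defined as a simple average of all observed values from Day 9 until Day 15".

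**The concern.** A window of Days 2 to 22 is harmless for an assessment made only at clinic visits, apart from early-termination visits. Applied to a diary filled in every day, it holds up to 14 candidate scores before the Week 2 visit is over, and any one of them stops the subject from being missing. The two rules written for absent data, non-response after dropout and multiple imputation otherwise, then have nothing to act on.

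Three things make this more than tidiness. The test carries familywise alpha and steers the rest of the sequence. The result can contradict the protocol's rule for withdrawn subjects. And early scores are not neutral between arms: of the 200 mg group in Phase 2b, Protocol 1.2.4 reports "Significant separation from placebo was achieved for the pruritus NRS score as early as 2 days after initiation of treatment". If that repeats, an early dropout who would be a non-responder under the protocol can become a Week 2 responder, more often on drug than on placebo.

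**Working it through.** **Plan figures.** The documents give no NRS4 response rate, NRS4 power, dropout rate or count of missing diaries, so there is no plan figure to reproduce on this point. The stated power for IGA and EASI-75 is not at issue.

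**Step 1: apply the rule as written.** Keep the entry within Days 2 to 22 that is nearest Day 15, and the later one if tied.

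| Diary pattern | Day used as Week 2 | Days early |
|---|---|---|
| Complete to Day 15 | 15 | 0 |
| Lost from Day 15 on | 14 | 1 |
| Last entry Day 11, nothing on Days 12 to 19 | 11 | 4 |
| Last entry Day 8, no later entry in the window | 8 | 7 |
| Last entry Day 6, no later entry in the window | 6 | 9 |
| Last entry Day 2, no later entry in the window | 2 | 13 |

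Of the 14 diary days in the window (Days 2 to 15), 12 (Days 2 to 13) lie outside the protocol visit window of Days 14 to 16.

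**Step 2: compare the rules for a Day 6 dropout.** Under Protocol 9.2.3 and 9.2.4 this subject is a Week 2 non-responder. Under SAP 5.3.1 with Appendix 2 the Day 6 score is mapped first, so nothing is missing at Week 2 and non-response is not applied. The sensitivity analysis in SAP 6.3.1 sets all missing data to non-response. It gives the same answer for this subject, because the mapped value is not missing.

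**Step 3: what can be said about size.** Every input below is an assumption. Let *f* be the share of an arm with only an early in-window entry and *r* the NRS4 rate at that entry.

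- *Dropouts, against the non-responder rule.* Shift in an arm's Week 2 rate = *f* × *r*. With *f* from 2% to 10% and *r* from 10% to 40%, the shift runs from 0.02 × 0.10 = 0.2 points to 0.10 × 0.40 = 4.0 points.
- *Effect on the test.* Suppose both arms have a true rate of 15% under the non-responder rule, *f* = 10%, and early rates of 30% (drug) and 5% (placebo). The windowed rates are 15 + 3.0 = 18.0% and 15 + 0.5 = 15.5%. With 150 and 75 subjects and a pooled two-sided test at 2.5%, the rejection probability is 3.8%. With early rates of 40% and 10% it is 4.4%. At *f* = 5% the two figures are 2.8% and 2.9%.
- *Diary gaps in subjects still in the study.* Here the early rate replaces the Day 15 rate, so the between-arm difference changes by *f* × (early difference − Day 15 difference). Take straight-line response from 10% to 45% (drug) and 3% to 15% (placebo) over Days 2 to 15. The mean over Days 2 to 11 is 10 + 35 × 4.5/13 = 22.1% and 3 + 12 × 4.5/13 = 7.2%, an early difference of 15.0 points from the unrounded values. At *f* = 10% the change is 0.10 × (15.0 − 30.0) = −1.5 points.
- *The same curves for dropouts.* Against non-response the change is 0.10 × 15.0 = +1.5 points.

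On one set of curves the two mechanisms are about equal and opposite. The net sign depends on the mix of dropouts and diary gaps, which the documents do not give.

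**The case against.** The strongest reply is that Appendix 2 chooses among visits, and a home diary entry on Day 6 is not a visit. The device-failure text in SAP 5.3.1 fits that reading. It treats NRS as missing at the scheduled Week 2 visit and later, and plans multiple imputation for it. If any entry from Days 2 to 14 could fill Week 2, there would be little at Week 2 to impute. This stands as a possible reading, so a reader should not infer that a bypass of both missing-data rules is settled. But the SAP nowhere states the restriction, and mapping all observed data points the other way. Two programmers could build different Week 2 datasets, and different counts against the threshold of 5 or fewer missing subjects per group that switches imputation off.

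A reader might also infer that the device failure pushes very early scores into Week 2. The documents do not support that: the failure is described from Day 15 on, and such subjects would normally have a Day 14 entry, inside the protocol window.

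Nor do the documents support a claim that the window dilutes the effect or costs power by a known amount. That follows only if affected subjects are compared with complete data. Against non-response for dropouts, the same assumed curves move the other way.

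The per-protocol analysis requires observed Week 12 IGA and EASI and so leaves out early dropouts who lack them. It is supportive and does not repair the full-analysis-set test. Calling the rule last observation carried forward would overstate it, since no score is used beyond its own window and the daily-diary problem is confined to Week 2.

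**Conclusion.** The point holds in limited form. As written, the SAP permits a diary score from any of Days 2 to 13 to serve as the Week 2 NRS4 result when nothing nearer Day 15 exists. For a subject who has already dropped out, this contradicts the protocol's non-responder rule on an alpha-controlled test, and the planned sensitivity analysis would not reveal it. The conclusion rests on reading the mapping sentence in SAP 5.3.1 literally; if visits-only was intended, the defect is that the SAP does not say so.

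The subjects at issue are mainly early dropouts and those with early diary gaps. How many there are, and the size and net direction of the effect, cannot be derived from the documents. The figures above show only that the dropout part could favour drug if itch improves early. The change is worth making before unblinding because it removes an ambiguity in a gatekeeping endpoint, not because a measured bias has been shown.

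**What to change.** Add an NRS-specific Week 2 row to SAP Appendix 2:

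1. Tie it to the protocol visit, Day 15 ±1 (Days 14 to 16), or to a modestly wider range fixed in advance. Use the entry nearest Day 15.
2. State that entries outside the range do not count as Week 2. For subjects who dropped out before Week 2, state that entries made before or at an early-termination visit do not count either. The range alone is not enough: Protocol 6.4 allows the end-of-treatment visit up to one week after the last dose, so a subject whose last dose was on Day 8 could record an NRS on Day 15.
3. Let the existing rules then apply: non-response after dropout, multiple imputation for other gaps.
4. Report per arm how many subjects have their only Days 2 to 22 entry outside the range.

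A complete diary still gives Day 15, and a diary lost from Day 15 still gives Day 14. The cost is one table row, two sentences and one count table. The downside is that a few more subjects are imputed or counted as non-responders at Week 2. It also reopens, for this endpoint only, the gaps that the latest window revision was meant to close.
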